3. SUBJECT POPULATIONS

3.1. Population Definitions

- Intent-to-Treat (ITT):** The ITT population will include all randomized subjects. Subjects who are randomized but not treated due to procedural screen failures will be included as part of ITT population.
- Modified Intent-to-Treat (mITT):** The Modified ITT will include all subjects in ITT who received the insert in the study eye, investigational product (IP) (OTX-DED or HV). The mITT population will be used as the primary efficacy analysis population and will also be used for all efficacy endpoints. Analyses performed on the mITT population will be according to the treatment the subject are randomized.
- Per Protocol (PP):** The PP population will include all mITT subjects who do not have any major protocol deviation which is likely to seriously affect the safety and efficacy outcomes of the study and who do not report excessive artificial tear use defined as greater or equal to 30 drops between Insertion/Day 1 (Visit 2) and Week 2 (Visit 4). Analysis on the PP population will be used as secondary efficacy analysis and will be performed for select efficacy endpoints, analyzing subjects under the treatment actually received. Important protocol deviations will be identified prior to locking the study database.
- Safety:** The Safety population will include all randomized subjects who received Investigational Product (IP) (OTX-DED or HV). Analyses performed on the Safety population will be according to the treatment the subject actually received.

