7.4 Procedural Exclusion Criteria

Subjects are considered procedural screen failures if the investigator is unsuccessful at placing the OTX-DED or HV intracanalicular ophthalmic insert in both eyes (i.e. neither eye has an insert). Subjects will be followed per protocol if the investigator successfully places one insert.

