9.4 Monitoring and Recording of AEs and SAEs

9.4.1 Adverse Events

Any AE experienced by the subject from Visit 2 (Insertion/Day 1) through Visit 7 (Week 8) is to be recorded in the eCRF, regardless of the severity of the event or its relationship to study treatment.

Any AEs already documented at a previous assessment and designated as ongoing, should be reviewed at subsequent visits as necessary. If these have resolved, this should be documented.

Changes in intensity or frequency of AEs should be recorded as separate events (i.e., a new record started).

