10.10 Subject Population(s) for Analysis

Intent-to-Treat (ITT): The ITT population will include all randomized subjects. Analysis on the ITT population will be used as the primary efficacy analysis and will be performed for all efficacy endpoints, analyzing subjects under the treatment to which they were randomized.

Per Protocol (PP): The PP population will include all ITT subjects who do not deviate from the protocol in any way likely to seriously affect the efficacy outcomes of the study. Analysis on the PP population will be used as secondary efficacy analysis and will be performed for select efficacy endpoints, analyzing subjects under the treatment actually received. Important protocol deviations will be identified prior to locking the study database.

Safety: The Safety population will include all subjects who received IP (OTX-DED or HV). Analyses performed on the Safety population will be according to the treatment the subject actually received.

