4.4. Subject Disposition

A summary of subject disposition will be tabulated, including the number screened, screened failure, and procedural screen failures will be presented. Subjects are considered procedural screen failures if the investigator is unsuccessful at placing the OTXDED or HV intracanalicular ophthalmic insert in both eyes (i.e. neither eye has an insert). Procedural screen failures will be exited from the study at that time, and will be included in the disposition tables as 'randomized, not treated'. Subjects will be followed per protocol if the investigator successfully places one insert.

The number and percentage of subjects included in each of the analysis populations (ITT, mITT, PP, Safety) will be presented by treatment groups and overall. Subject disposition events including randomization, treated, completed study, withdrawal prior to completing the study, and reasons for withdrawal will be summarized by treatment groups and overall.

A by-subject listing of study completion information, including the reason for premature study withdrawal, if applicable, will be presented.

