4.9. Safety Analyses

All safety analyses will be conducted on the Safety population.

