4.9.1. Adverse Events

Adverse events will be coded using MedDRA Version 24.0 – Mar 2021 and displayed in tables and listings using System Organ Class (SOC) and Preferred Term (PT).

Analyses of adverse events will be performed for those events that are considered treatment emergent adverse events (TEAE), where treatment emergent is defined as any adverse event

Statistical Analysis Plan

Sponsor:	Ocular Therapeutix, Inc.		
Protocol:	OTX-DED-2020-201		
Document Version No.:	V1.0	Document Date:	11NOV2021

with onset on or after the first dose of study medication through the end of the study or any event that was present at baseline but worsened in intensity or was considered drug-related by the investigator through the end of the study.

The safety will be assessed by incidence of TEAEs, therefore, in any tabulation, a subject contributes only once to the count for a given adverse event (SOC or preferred term). An overall summary of TEAEs will be presented including the number of events and the number of the subjects with events along with percentages by treatment group and overall. The overall summary will include subjects with AE leading to death, subjects with TEAEs leading to insert removal and subjects with TEAEs leading to subject withdrawal. In summary tables, SOC will be presented alphabetically and events within SOC will be presented by decreasing frequency count based on the total column.

The frequency and percentage of subjects with any TEAE, any serious TEAE, any TEAEs by relationship to treatment (unrelated, related), any serious TEAEs by relationship to treatment (unrelated, related), any TEAE by severity (mild, moderate, or severe) will be summarized separately for ocular and non-ocular events by treatment group and overall. Separate summaries for ocular TEAEs and non-ocular TEAEs by preferred terms in decreasing frequency based on all subjects will be tabulated.

All adverse events will be listed in subject data listings.

By-subject listings also will be provided for the following: subject deaths; serious adverse events; and adverse events leading to withdrawal.

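### Adverse events from an insertion attempt that fails in both eyes enter no AE summary table, because of both the Safety population and the TEAE definition; one supplementary table would close the gap (low severity)

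*SAP*

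**What the plan says.** **Order of events.** Protocol 8.4 requires procedures in the order listed, and 8.4.2 lists randomisation before insert placement.

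**Failure in both eyes.** Protocol 7.4: "Subjects are considered procedural screen failures if the investigator is unsuccessful at placing the OTX-DED or HV intracanalicular ophthalmic insert in both eyes", meaning that neither eye has an insert. SAP 3.1: "Subjects who are randomized but not treated due to procedural screen failures will be included as part of ITT population". SAP 4.4: "Procedural screen failures will be exited from the study at that time, and will be included in the disposition tables as" randomised and not treated. A subject with one successful insert is followed as normal.

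**Safety population.** Protocol 10.10: "The Safety population will include all subjects who received IP (OTX-DED or HV"). SAP 3.1 applies the same restriction to randomised subjects: "The Safety population will include all randomized subjects who received Investigational Product (IP) (OTX-DED or HV"). SAP 4.9: "All safety analyses will be conducted on the Safety population".

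**AE tables.** SAP 4.9.1 analyses treatment-emergent AEs (TEAEs): those with onset from the first dose onward, or present at baseline and then worsened or judged drug-related. It adds: "All adverse events will be listed in subject data listings". It also provides by-subject listings of serious AEs and of AEs leading to withdrawal.

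**Recording.** Protocol 9.4.1: "Any AE experienced by the subject from Visit 2 (Insertion/Day 1) through Visit 7 (Week 8) is to be recorded in the eCRF", whatever the severity or relationship. Protocol 8.4.2 and footnote 7 of Appendix 1 send findings before insertion to medical history.

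**The procedure as a source of harm.** Protocol 4.4 has a separate list of AEs and risks seen with the insertion procedure. Protocol 9.7.2 judges relatedness against the procedure as well as the insert.

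**The concern.** The protocol treats the insertion procedure as a hazard in its own right, and the suggested technique in Appendix 11 dilates the punctum and canaliculus before any insert goes in. A subject can therefore undergo the procedure and still be classed as untreated. Procedure-related AEs are tabulated only for subjects with at least one successful placement, so those in whom placement failed completely leave both numerator and denominator. That exclusion is not random with respect to the procedure.

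At stake is the completeness of procedural safety reporting, in a trial whose sample size is justified partly by the safety information it will yield (Protocol 10.3, SAP 4.1). Efficacy is not involved.

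**Working it through.** The plan states no figure on this point, so the main check follows one subject through the definitions.

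1. The subject is randomised and insertion is attempted in both eyes without success. Under Protocol 7.4 this is a procedural screen failure.
2. Under SAP 3.1 and 4.4 the subject is in ITT, counted in disposition as randomised and not treated, and exited.
3. **First bar.** Safety requires receipt of IP (Protocol 10.10, SAP 3.1), and all safety analyses use Safety (SAP 4.9). The subject is outside every AE table.
4. **Second bar.** AE tables count TEAEs. A new event from the attempt cannot have onset on or after a first dose that never took place, and it was not present at baseline. A baseline condition made worse by the attempt could meet the second limb of the definition. So could an event judged drug-related, if that phrase is read without the baseline condition. The first bar would still exclude both.
5. **What remains.** The AE and SAE listings in SAP 4.9.1 name no population, so they can show the event if it was recorded as an AE. SAP 4.9 could, however, be read as confining listings to Safety too.
6. **If it is recorded as history instead.** The medical-history summaries in SAP 4.5.2 use mITT, which requires an insert in the study eye, so they exclude the subject as well.

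**Weight of one event.** Input: 50 subjects planned per arm (SAP 2.1). Assume one both-eye failure with one procedure-related AE, and no other such AE in the arm.

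- Safety table: 0/(50 − 1) = 0/49 = 0.0%.
- All attempted insertions: 1/50 = 2.0%.
- Same event over the whole trial, with no other such AE: 0/149 = 0.0% against 1/150 = 0.67%.

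**How many subjects could be affected.** The documents give no both-eye failure rate, so the rates p below are assumptions. With 150 randomised, the expected number is 150 × p and the chance of at least one is 1 − (1 − p)^150.

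| Assumed p | Expected subjects | Chance of at least one |
|---|---|---|
| 0.5% | 0.75 | 0.53 |
| 1% | 1.5 | 0.78 |
| 2% | 3.0 | 0.95 |
| 5% | 7.5 | above 0.99 |

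These are subjects outside the AE tables, not AEs. No harm rate after a failed attempt is given, so the number of missing AEs cannot be computed.

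**Second-eye attempts, a separate matter.** When only one eye is fitted on Day 1, Protocol 8.4.2 calls for AE review of the second eye at the return visit only if that insertion succeeds. Footnote 3 of Protocol Appendix 1 and of SAP Table 2 repeats AEs at that visit without the condition. These subjects already have one insert and are in Safety, so this is a recording mismatch and not part of the omission.

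**The case against.** A Safety population defined by receipt of product is normal, and the protocol and SAP agree on it. For rates among treated subjects, leaving out someone who received nothing is what the definition intends, and it does not bias those rates. Recorded events are still listed by subject, failures are counted in disposition, and SAEs are reported within 24 hours and followed (Protocol 9.5, 9.4.2). Either canaliculus may be used, a spoiled insert may be replaced, and some anatomical obstacles are exclusion criteria, so complete failure may be rare. Some procedure risks in Protocol 4.4, such as inability to remove the insert, presuppose a placed one. Protocol 9.4.1 already requires any AE from Visit 2 to be recorded.

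All of that stands, and it is why the point is minor. What survives is narrow: a listing gives no rate by arm, and disposition shows failures but not harm.

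Three stronger readings are tempting and not supported:

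- **That these events are lost or concealed.** The listings can show them, and no passage says that an event from an attempt is not an AE. The text on findings before insertion simply leaves the case unaddressed.
- **That the Safety definition is the sole cause, so that widening it would suffice.** The first-dose anchor would still exclude new events.
- **That the arms are affected unequally because dry insert diameters differ.** The documents do not link diameter to placement failure. They neither show an imbalance nor rule one out.

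**Conclusion.** The gap is real but small in scope. A new AE from an insertion attempt that fails in both eyes enters no AE summary table, for two independent reasons: the Safety population requires receipt of IP, and treatment-emergence is anchored to a first dose. This rests on the SAP's own label of not treated for these subjects, which places them outside Safety even though receipt of IP is not defined for an insert tried and discarded.

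The size is unknown and probably small. The 0/49 against 1/50 comparison shows what one event would weigh; it does not estimate how often one occurs. A reader might infer that the trial's safety rates are wrong. They are not: rates among treated subjects and all efficacy results are unaffected. What is missing is a complete denominator for procedure-related harm. Severity is low, and the change is optional.

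**What to change.** 1. Keep the Safety population as defined.
2. Add one supplementary descriptive table of procedure-related AEs in all randomised subjects with an attempted insertion. Count events from the first attempt, not the first dose. Class subjects by treatment received, or by assigned arm where no insert was placed.
3. State in SAP 4.9.1 that the AE and SAE listings include these subjects.
4. State that an event arising from an insertion attempt is an AE and not medical history from before insertion (Protocol 8.4.2 and Appendix 1, footnote 7).
5. Separately, reconcile Protocol 8.4.2 with footnote 3 of Protocol Appendix 1 and SAP Table 2 on AE review for a second-eye attempt.

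**Cost.** Items 2 and 3 need one table and some SAP wording, with no model. Items 4 and 5 touch protocol text, and amendments need IRB approval (Protocol 13), but the table does not depend on them. The drawback is that the new table mixes assigned and received treatment and includes a few subjects with short follow-up; a footnote should say so.

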3.2. Protocol Deviations

At the discretion of the sponsor, major protocol deviations as determined by a review of the data prior to unmasking of the study results and the conduct of statistical analyses may result in the removal of a subject's data from the PP Population. This file will include a description of the protocol deviations, as well as classification of major or minor. It will be finalized prior to hard database lock and unmasking. Major protocol deviations will be summarized by treatment groups and overall. The data listing for all protocol violations will be also presented.

Sponsor:	Ocular Therapeutix, Inc.		
Protocol:	OTX-DED-2020-201		
Document Version No.:	V1.0	Document Date:	11NOV2021

4. STATISTICAL METHODS

4.1. Sample Size Justification

This study is not powered to show statistical significance but will provide initial estimates and trends of the endpoints for use in future trial designs. The sample size will allow for safety information to be obtained, while still limiting the number of subjects exposed to the IP. Statistical analyses will be descriptive.

The trial will include approximately 150 subjects (300 eyes) from approximately 15 sites.

4.2. General Statistical Methods and Data Handling

4.2.1. General Methods

All output will be incorporated into Microsoft Excel or Word files, sorted, and labeled according to the International Council on Harmonisation (ICH) recommendations, and formatted to the appropriate page size(s).

Tabulations will be produced for appropriate demographic, baseline, efficacy, and safety parameters. For categorical variables, summary tabulations of the number and percentage of each category of the parameter will be presented by treatment groups and visits (as applicable). For continuous variables, the n, mean, standard deviation, median, minimum, and maximum values will be presented.

The baseline visit will be defined as the last non-missing measure prior to initiation of IP. Differences between treatment groups will be calculated as OTX-DED minus HV and change from baseline will be calculated as follow up visit minus baseline visit values. In addition to looking at the individual formulations, the two formulations of OTX-DED will be combined and summarized.

All statistical testing will be done at the two-sided alpha level of 0.05, with no adjustments due to multiple endpoints testing.

Sponsor:	Ocular Therapeutix, Inc.		
Protocol:	OTX-DED-2020-201		
Document Version No.:	V1.0	Document Date:	11NOV2021

4.2.2. Unit of Analysis

Both eyes will be treated with the same treatment/formulation. The study eye and non-study eye will be determined at the time of programing as follows. If both eyes qualify, the eye having the highest (worst) grading score among Nasal, Temporal, and Frontal zones from the photographic assessment of conjunctival hyperemia at baseline will be designated as the study eye and the other eye will be designated as the non-study eye. If both eyes have the same photographic assessment conjunctival hyperemia the highest (worst) grade score, the right eye will be the study eye. If only one eye qualifies, that eye will be the study eye, but both eyes will still receive the same treatment/formulation and be included in the safety analysis. If only an insert is successfully placed in one eye, then that eye will be the study eye, if it qualifies for the study.

The unit of analysis will be the study eye (primary study eye) with the worst zone chosen for bulbar conjunctival hyperemia summaries and analyses. If there are equal scores in two or more zones, the worst zone will be selected in a preferential order with Nasal zone being the most preferred, followed by Temporal zone, and then by Frontal zone. Efficacy summaries will be presented for both study and non-study eyes. Safety summaries will include summaries of both study and non-study eyes. All primary, sensitivity, secondary, and exploratory endpoints will be analyzed for both study and non-study eyes, separately. All summaries will be presented by treatment groups and visits, where appropriate. In addition to looking at the individual formulations, the two formulations of OTX-DED will be combined and summarized.

4.2.3. Computing Environment

All descriptive statistical analyses will be performed using SAS statistical software (Version 9.4), unless otherwise noted. Medical History and adverse events will be coding using Medical Dictionary for Regulatory Activities (MedDRA) version 24.0 - Mar 2021. Concomitant medications will be coded using World Health Organization (WHO) DD B3 WHO Drug DDE – Sep 2020.

4.2.4. Methods of Pooling Data

The two OTX-DED formulations will be presented separately as individual formulations and combined.

Sponsor:	Ocular Therapeutix, Inc.		
Protocol:	OTX-DED-2020-201		
Document Version No.:	V1.0	Document Date:	11NOV2021

4.2.5. Adjustments for Covariates

The baseline value will be included in the analysis of covariance (ANCOVA) model as a covariate for adjustment.

4.2.6. Multiple Comparisons/Multiplicity

To control the type I error for the hypothesis testing of the primary endpoint, least square means will be used to make treatment comparisons using Dunnett's adjustment for multiple comparisons to a control.

As this is a Phase 2 study, no adjustments to alpha will be made for testing of multiple endpoints.

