	
Primary Hypothesis: Statistical hypothesis for the primary efficacy endpoint of photographic assessment of bulbar conjunctival hyperemia at 15 days is as follows: H_0: There is no difference in mean change from baseline in photographic assessment of bulbar conjunctival hyperemia grades between OTX-DED and HV treated subjects at 15 days. H_{1a}: There is a difference in mean change from baseline in photographic assessment of bulbar conjunctival hyperemia grades between OTX-DED and HV treated subjects at 15 days.
 
Primary Efficacy Analyses: The primary efficacy analyses will be conducted on the intent-to-treat (ITT) population with multiple imputation using Markov Chain Monte Carlo (MCMC) for missing data.
 
An analysis of covariance (ANCOVA) model will be run to estimate least square (LS) treatment means. This model will include the baseline value as a covariate for adjustment and treatment group as the sole factor. LS means will be used to make treatment comparisons using Dunnett's adjustment for multiple comparisons to a control. Statistical significance of treatment differences will be determined using a two-sided significance level of $\alpha = 0.10$. Two-sample t-tests will be used as an unadjusted sensitivity analysis, as well as non-parametric Wilcoxon rank sum tests. If both OTX-DED treatment groups have similar results, they will be combined and compared to HV using a two-sample t-test and Wilcoxon rank sum test. Sensitivity analyses will be conducted on the ITT population with last observation carried forward (LOCF), as well as using observed data only for the ITT and per protocol (PP) populations.
 
Secondary Efficacy Analyses: The secondary efficacy endpoints including change from baseline of: severity of eye dryness score at 15 days, frequency of eye dryness score at 15 days, severity of eye dryness score at each post-baseline visit, frequency of eye dryness score at each post-baseline visit, investigator assessment of bulbar conjunctival hyperemia at each post-baseline visit, total corneal fluorescein staining (tCFS) at each post-baseline visit, CFS sub-regions at each post-baseline visit, Ocular Surface Disease Index questionnaire (OSDI[®]) at each post-baseline visit (total score, each of the three domains, and individual questions) and SPEED questionnaire (overall score and individual questions), CFB at each post-baseline visit will be analyzed in a manner similar to the primary efficacy variable using ANCOVA model. The secondary efficacy analyses of severity of eye dryness scores, frequency of eye dryness scores and photographic assessment of bulbar conjunctival hyperemia will be analyzed in a similar manner as the primary efficacy analyses. The remaining secondary efficacy analyses will be conducted using observed data only on the ITT and PP populations.

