4.7.1. Primary Analyses

For the primary efficacy endpoint analyses of change from baseline in photographic assessment of bulbar conjunctival hyperemia (evaluated by central reading center) worst zone in the study eye at Visit4 (Day 15) (as defined in section 2.6.1.1), the following modeling and analyses will be performed on mITT population, observed data:

An analysis of covariance (ANCOVA) model will be run to estimate least square (LS) means treatment. This model will include the baseline value as a covariate for adjustment and treatment group as the sole factor. Least square means will be used to make treatment comparisons using Dunnett's adjustment for multiple comparisons to a control. Statistical significance of treatment differences will be determined using a two-sided significance level of $\alpha = 0.05$.

In the ANCOVA model, LS means treatment group comparison of OTX-DED 0.2 mg to HV, OTX-DED 0.3 mg to HV, and Overall OTX-DED (combined OTX-DED 0.2 mg and OTX-DED 0.3 mg using sample size weights of OTX-DED 0.2 mg and OTX-DED 0.3 mg groups as coefficients for the parameters) to HV will be reported. Unadjusted treatment group analyses using two-sample t-test and Wilcoxon rank sum test will be run on these treatment group combinations.

Each bulbar conjunctival hyperemia zone (Nasal, Temporal, and Frontal) and the Total of the three zones in study eye will be analyzed in a manner similar to the primary efficacy variable as described above.

The same analyses will be done for the non-study eye. For non-study eye, the worst zone similar to worst zone in study eye (details in section 2.6.1.1) will be independently determined using photographic assessment bulbar conjunctival hyperemia in non-study eye at baseline.

Sponsor:	Ocular Therapeutix, Inc.		
Protocol:	OTX-DED-2020-201		
Document Version No.:	V1.0	Document Date:	11NOV2021

The primary efficacy endpoints will also be analyzed on PP population.

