7.1.4. SAS codes to run t-test on MI data

```

/* SAS code below for testing group 1 vs group 3*/
ods output statistics=ttest1;
proc ttest data=din;
  where TRTPN in (1 3) ;
  by AVISIT PARAMN INPUT;
  class TRTPN;
  var CHG;
run;

ods output parameterestimates=pdif;
proc mianalyze data=ttest2;
  modeleffects mean;
  stderr stderr;
  by AVISIT PARAMN Class;
run;

```

7.1.5. SAS codes to run ANCOVA (using PROC MIXED) on Observed data and LOCF

Sponsor:	Ocular Therapeutix, Inc.		
Protocol:	OTX-DED-2020-201		
Document Version No.:	V1.0	Document Date:	11NOV2021

```
*** PROC MIXED ***;
ods output LSMESTIMATES=ls1(rename=(label=PARAMETER)) DIFFS=dun1;
proc mixed data=din;
by PARAMN AVISITN;
CLASS TRTPN (ref=last);
MODEL CHG=TRTPN BASE;
lsmeans TRTPN / cl pdiff=control('3') adjust=Dunnett;
LSMESTIMATE TRTPN "OTX-DED 0.2MG" 1 0 0,
"OTX-DED 0.3MG" 0 1 0,
"Overall OTX-DED" &WG1. &WG2. 0,
"HV" 0 0 1,
"OTX-DED 0.2MG vs HV" 1 0 -1,
"OTX-DED 0.3MG vs HV" 0 1 -1,
"Overall OTX-DED vs HV" &WG1. &WG2. -1 / cl;
run;
```

7.1.6. **SAS codes to output 95% CI for proportions using Clopper-Pearson method and 95% CI for the proportion difference using Chan and Zhang (1999) method using observed and LOCF data**

```
ods output RiskDiffCol1=freq1(where=(ROW in ("Row 1" "Row 2" "Difference")));
FishersExact=freq2(where=(NAME1="XP2_FISH"));
proc freq data=din;
where TRTPN in (1 3) and avisitn=4;
table TRTPN*AVALN / norow nocol nopercent fisher;
exact riskdiff(method=score);
run;
```

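### The two dose-versus-vehicle tests of the primary endpoint use single-step Dunnett; step-down Dunnett holds the same 5% error for these two contrasts and adds up to about 10 points to the chance of showing both doses

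*SAP*

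**What the plan says.** SAP 4.2.6 states the purpose as "To control the type I error for the hypothesis testing of the primary endpoint" and the method as "least square means will be used to make treatment comparisons using Dunnett's adjustment for multiple comparisons to a control". SAP 4.7.1 repeats the method for the Day 15 photographic hyperemia endpoint and sets the two-sided level at 0.05. SAP 4.2.1 gives the same level: "All statistical testing will be done at the two-sided alpha level of 0.05, with no adjustments due to multiple endpoints testing".

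The code for observed and LOCF data in SAP 7.1.5 is "lsmeans TRTPN / cl pdiff=control('3') adjust=Dunnett". This is the single-step procedure: each dose is compared with vehicle against one common Dunnett critical value. Neither document mentions a step-down rule.

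The same code also estimates each dose against vehicle, and the two doses pooled against vehicle, through LSMESTIMATE with confidence limits and no multiplicity adjustment.

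On size, SAP 4.1 says: "The trial will include approximately 150 subjects (300 eyes) from approximately 15 sites". Protocol 10.3 and SAP 4.1 add that the study is not powered for significance and that analyses will be descriptive. No effect size, SD or power is given.

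**The concern.** Only two hypotheses are in the Dunnett family. Once the dose with the larger |t| has passed the Dunnett value, at most one true null can remain. By closed testing, the other dose can then be tested at its unadjusted 0.05 without raising the familywise error above 5%. The single-step rule still holds the second dose to the stricter cut-off.

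What is at stake is the chance of showing both doses. A second dose with a nominal p between about 0.027 and 0.05 would be called non-significant when it need not be, and that near miss could be misread as a difference between doses.

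**Working it through.** The documents contain no power figure to reproduce, so the two rules are compared directly.

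**Inputs from the documents**
- 50 subjects per arm (SAP 2.1, Table 1), allocated 1:1:1 (SAP 2.3).
- ANCOVA with three groups and one covariate (SAP 4.7.1): error df = 150 − 4 = 146.
- Two-sided alpha of 0.05 (SAP 4.2.1 and 4.7.1).

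**Assumptions**
- True effect δ of 0.2 to 1.0 residual SD, equal in both doses unless stated.
- All 50 per arm evaluable, with 45 and 40 as checks.

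**Set-up.** Each contrast has standard error SD × √(2/50) = 0.2 SD, so its test statistic is centred at δ/0.2 = 5δ. The two contrasts share the vehicle arm: covariance SD²/50 over variance 2·SD²/50 gives a correlation of 0.5.

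**Critical values.** The Dunnett value c solves P(max|T| ≤ c) = 0.95 with correlation 0.5 and df 146. By numerical integration c = 2.234, a nominal p of 0.027. The unadjusted value is t(0.975, 146) = 1.976.

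**Rules**
- Single-step shows both doses if both |t| > 2.234.
- Step-down shows both if the larger |t| > 2.234 and the smaller |t| > 1.976.
- Both rules show at least one dose exactly when the larger |t| > 2.234, so that probability is the same under either.

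**Error rate** (simulation, 2 million draws per scenario)
- Both nulls true: 4.98% under either rule.
- One null true, the other dose with a very large effect (1.5 or 3 SD): false rejection is 2.7% under single-step and 5.0% under step-down. The 2.7% shows the part of the 5% allowance that single-step leaves unused.

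**Chance of success, equal effects, 50 per arm**

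| Assumed effect (SD) | Both doses, single-step | Both doses, step-down | Gain (points) | At least one dose, either rule |
|---|---|---|---|---|
| 0.2 | 3.8% | 6.2% | 2.4 | 18.6% |
| 0.3 | 11.1% | 16.4% | 5.3 | 35.9% |
| 0.4 | 25.0% | 33.3% | 8.4 | 57.0% |
| 0.5 | 44.7% | 54.7% | 10.0 | 76.5% |
| 0.6 | 65.7% | 74.5% | 8.8 | 89.7% |
| 0.7 | 82.7% | 88.5% | 5.8 | 96.5% |
| 0.8 | 93.0% | 95.9% | 2.9 | 99.1% |
| 1.0 | 99.4% | 99.7% | 0.3 | 100.0% |

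Gains are taken before rounding. Power for a single dose at 0.5 SD goes from 60.6% to 65.6%.

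**Sensitivity**
- With 45 or 40 evaluable per arm, the peak gain is still 10.0 points, at about 0.55 SD.
- Unequal effects: 0.3/0.5 SD gains 7.6 points, 0.4/0.6 gains 9.8, 0.5/0.7 gains 9.6 and 0.5/1.0 gains 9.4. The largest gain found was about 10.2.
- The protocol synopsis gives alpha as 0.10, against 0.05 in Protocol 10.4 and 10.7 and in the SAP. At 0.10 the gain is 10.3 points at 0.4 SD, 10.2 at 0.5, 7.5 at 0.6 and 4.1 at 0.7.

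**The case against.** The strongest reply is that nothing here is an error. Dunnett's adjustment was set in the protocol and kept in the SAP. The single-step form controls the error it claims to control, and its tests agree with its simultaneous intervals. In a trial meant to provide estimates, that agreement is worth something. Neither document makes significance of both doses a success criterion. All of this stands. It makes the change optional; it does not remove the gain.

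Three stronger readings are tempting, and the documents do not support them.

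- A reader might infer a flat gain of 10 points. That is essentially the maximum, near an assumed 0.5 SD, and no effect size is stated.
- A reader might divide dose by duration (0.2/14 and 0.3/21 are both about 0.014 mg per day) and conclude that the doses must act alike up to Day 15, so the gain will be near its peak. Protocol 4.2 describes a sustained and then tapered release, for up to 14 days with one insert and up to 21 with the other. The primary visit at Day 15 ± 2 days falls around the nominal end of the first period and inside the second. Equal effects are therefore an assumption. The unequal pairs above show that the gain does not depend on it.
- A reader might infer that unadjusted intervals will be printed beside Dunnett p-values. The LSMESTIMATE limits are indeed 1 − 1.976/2.234 = 11.5% narrower. But the code also requests the Dunnett limits and saves them in the differences table, and nothing in the SAP pairs the unadjusted limits with the adjusted p-values. At most, the SAP should name which limits are reported.

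The proposed rule also has a cost: the second dose can be significant while its Dunnett interval includes zero.

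**Conclusion.** The point holds as an efficiency suggestion. For the two individual-dose contrasts, step-down Dunnett rejects whenever single-step does, sometimes rejects more, and keeps the familywise error at 5%. The benefit is confined to showing both doses, and its size depends on an effect that the documents do not give: 8 to 10 points at 0.4 to 0.6 SD, falling away on either side. The figures assume 50 evaluable per arm, approximately normal residuals with a common SD, and a two-sided alpha of 0.05.

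It would be wrong to conclude that the planned analysis is invalid. It would also be wrong to read the 5% as covering every test of the primary endpoint: under either rule, the pooled-dose comparison with vehicle sits outside the Dunnett family. Because the trial is declared unpowered and descriptive, the practical weight is modest.

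**What to change.** Optional, and to be settled before unmasking.

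1. In SAP 4.2.6 and 4.7.1, state the rule: test the dose with the larger |t| by its Dunnett-adjusted p; if p ≤ 0.05, test the other dose by its unadjusted two-sided p at 0.05; otherwise stop.
2. Name the Dunnett-adjusted limits from the LSMEANS differences table as the reported intervals for the two dose contrasts. Footnote that the second dose's interval may include zero when its step-down test is significant.
3. State that the pooled-dose contrast is not covered by this error control.

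The cost is a few sentences in the SAP, one footnote and a few lines of code. Sample size, data collection and point estimates do not change.
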